### (iii) Outcome Measures

The primary outcomes of this study are:

1. The 5-year incidence of CVD among RAMP-HT and usual care HT patients
2. The direct medical costs of RAMP-HT and usual care HT patients with and without complications
3. The ICER of cost per QALY gained by RAMP-HT compared to usual care group

The secondary outcomes of this study are:

4. The 5-year incidence of end stage renal disease (ESRD) and all-cause mortality among RAMP-HT and usual care HT patients
5. The hazard ratio of CVD, ESRD and all-cause mortalities between

RAMP-HT and usual care group

6. The Number-Need-to-Treat (NNT) to reduce one CVD, ESRD and mortality in 5 years by RAMP-HT

(iv) Data Collection

**HA CMS Data Extraction of Incidence of HT Complications and All-cause Mortality**

Our RAMP-HT QOC study will have collected anonymous 3-year follow up HA CMS data of the cohorts available by November 2015. This study plans to extend the follow up period for an additional 2 years to measure the 5-year incidence of CVD, ESRD and mortality outcomes of these HT patient cohorts from 1 Oct 2011 to 31 March 2017. The data extraction will be carried out by the HA statistics team. Each patient in the cohorts (RAMP-HT and usual care groups) will be observed from baseline to the first occurrence of any of the outcome events until 31 March 2017, with CMS documented diagnoses defined by the relevant ICPC-2 and ICD-9-CM codes below:

1. Cardiovascular disease (CVD) is defined as the presence of any of coronary heart disease (CHD), heart failure or stroke. CHD includes all ischaemic heart disease, myocardial infarction (MI), coronary death or sudden death as indicated by the ICPC-2 K74 to K76 or ICD-9-CM 410.x, 411.x to 414.x, 798.x codes. Heart failure is defined as the ICPC-2 K77 or ICD-9-CM 428.x codes. Stroke (fatal and non-fatal stroke) is defined by the ICPC-2 K89 to K91 or ICD-9-CM 430.x to 438.x codes.
2. End Stage Renal Disease (ESRD) is defined by any of ICD-9-CM 250.3x, 585.x, 586.x, or an estimated Glomerular Filtration Rate (eGFR)  $<15\text{mL/min}/1.73\text{m}^2$ , according to the definition of the National Kidney Foundation.
3. Mortality is defined by a documented death in the Hong Kong Death Registry.

The definitions of each HT complication are determined by the clinician co-investigators and endorsed by clinicians of the HA.

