##### **(ii) Subjects**

All patients who have enrolled into the RAMP-HT between 1 Oct 2011 and 31 March 2012, fulfilled the following inclusion criteria and without any exclusion criterion will be included in the RAMP-HT cohort. The same number of matched patients receiving usual care in GOPCs who have never enrolled into RAMP-HT on or before 31 March 2017, fulfilled the following inclusion criteria and without any exclusion criterion will be randomly selected from the HA clinical management system (CMS) to form the usual

care cohort.

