#### Inclusion criteria

1. Age  $\geq 18$  years old and  $<80$  years old
2. Coded with ICPC-2 of K86 on or before baseline\* (\*date of RAMP-HT enrolment for RAMP-HT cohort, and 31 March 2012 for usual care cohort)
3. Had uncontrolled blood pressure (i.e. average Systolic Blood Pressure (SBP)  $\geq 140$  mmHg OR Diastolic Blood Pressure (DBP)  $\geq 90$  mmHg between 6 months before and 3 months after baseline\*)

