#### *(ii) Direct Medical Costs of HT patients*

The medical cost analysis will focus on the direct medical costs involved in the care of HT patients without or with specific HT complications (i.e. CHD, heart failure, stroke and ESRD) in both public and private healthcare sectors; indirect cost (e.g. opportunity cost) and non-medical costs (e.g. transportation cost, carer cost) will not be measured.

Public medical costs will be estimated from products of the unit costs (published in the HKSAR Government Gazette and Hospital Authority ordinance (Chapter 113) of charges for non-entitled persons) and the utilization rates of 1) dispensed drugs (*note: self-financed drugs will be considered as private medical cost, see below*), 2) laboratory tests and investigations, 3) healthcare services including general outpatient clinics (GOPC), specialist outpatient clinics (SOPC), allied health services (e.g. dietician, physiotherapist or occupational therapist), accident and emergency (A&E) department and 4) admissions to hospital in the 12 months before baseline and at 12, 24, 36, 48 and 60 months after study enrolment for each patient in the study cohorts. The data extraction will be carried out by the HA statistics team.

Private direct medical costs include the cost of all private Western doctor and Chinese medicine practitioner consultations, private hospitalisation and self-medications inclusive of self-financed medications prescribed by the HA. 598 HT patients (307 RAMP-HT patients and 291 usual care patients) who were recruited from HA GOPCs for the longitudinal evaluation of patient reported outcomes (PRO) in the evaluation of QOC RAMP-HT study from May 2013 to March 2014 will be invited to complete a “private medical cost of HT questionnaire” (Appendix E) by telephone. The questionnaire is adapted from the costing questionnaire that was used in our in-depth study on the cost-effectiveness analysis of RAMP-DM that had proven feasibility and validity (HHSRF # EPC\_HKU-1A).

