**Long Term Effectiveness of RAMP-HT**

Descriptive statistics will be performed on the clinical parameters (e.g. blood pressure (BP), lipid profile, BMI) and incidence of CHD, heart failure, stroke, ESRD, HT-related mortality and all-cause mortalities of the RAMP-HT and usual care cohorts. Differences in each outcome between groups will be tested using independent t-tests for continuous variables such as mean BP, or chi-square tests for categorical variables such as proportion of patients with BP control or CVD incidence. The number needed to treat to reduce one CVD, each specific HT complication and death by RAMP-HT will be calculated from the unadjusted 5-year rates between RAMP-HT and usual care HT cohorts.

Multivariable Cox proportional hazards regression will be performed to estimate the adjusted effect of RAMP-HT on the dependent variable of each first HT complication event, adjusting for all baseline covariates of patients. Cox model has been widely used to evaluate the effectiveness of primary care intervention in previous study. For each model, survival curves will be estimated by Kaplan-Meier method and the differences between RAMP-HT and usual care groups will be compared using the

log-rank test. The effectiveness of RAMP-HT will be measured by Hazard ratio with 95% confidence intervals in the regression models. Predictive accuracy of Cox models will be assessed and compared using Harrell's discrimination C-index, ranging from zero to one. A value of 0.5 indicates no predictive discrimination, and values of 0 or 1.0 indicate perfect separation of patients. Goodness-of-fit for Cox regression model will be assessed using Akaike information criterion and Bayesian information criterion.

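### The crude 5-year CVD comparison and the NNT give RAMP-HT up to six more months at risk than usual care, because no 60-month cut is stated

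*Combined protocol and SAP*

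**What the plan says.** - **Enrolment (section d(ii), Subjects).** The RAMP-HT cohort is "All patients who have enrolled into the RAMP-HT between 1 Oct 2011 and 31 March 2012" who meet the eligibility criteria.
- **Baseline (Inclusion criteria, item 2).** It is the "date of RAMP-HT enrolment for RAMP-HT cohort, and 31 March 2012 for usual care cohort".
- **End of observation (section d(iv), HA CMS Data Extraction).** Each patient in either cohort "will be observed from baseline to the first occurrence of any of the outcome events until 31 March 2017". The same paragraph describes the target as the "5-year incidence of CVD, ESRD and mortality outcomes of these HT patient cohorts from 1 Oct 2011 to 31 March 2017".
- **Outcomes (section d(iii)).** The first primary outcome is "The 5-year incidence of CVD among RAMP-HT and usual care HT patients". The NNT over 5 years is a listed secondary outcome, as are the hazard ratios.
- **Analysis (Long Term Effectiveness of RAMP-HT).** Group differences are tested with "chi-square tests for categorical variables such as proportion of patients with BP control or CVD incidence". The NNT "will be calculated from the unadjusted 5-year rates between RAMP-HT and usual care HT cohorts". Kaplan-Meier curves with a log-rank test and adjusted Cox models are also planned.
- **Costs (Direct Medical Costs of HT patients).** Public costs are measured in the year before baseline and "at 12, 24, 36, 48 and 60 months after study enrolment for each patient in the study cohorts".

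**The concern.** The two cohorts share a closing date but not a starting date. A crude proportion of patients with an event by 31 March 2017 therefore covers a longer period for RAMP-HT than for usual care, and the imbalance falls on one group only. Neither the chi-square test nor an NNT taken from unadjusted rates corrects for this.

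5-year CVD incidence is a primary outcome and the basis of the sample size, and the NNT is the figure most likely to be quoted to policy makers. Both would be distorted against RAMP-HT, and both could disagree with the hazard ratio computed from the same patients.

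**Working it through.** **Time at risk, from the stated dates alone.** From 31 March 2012 to 31 March 2017 is 5.00 years, for every usual-care patient. From 1 October 2011 to 31 March 2017 is 5.50 years, so RAMP-HT patients have 5.00 to 5.50 years. The excess is 0 to 6 months and needs no assumption.

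**Inputs for the size.** From the sample size section: 5-year CVD risks of 7% (RAMP-HT) and 8% (usual care), 8,681 patients per group, and observed 1-year risks of 1.33% and 1.76%. Tests are two-sided at 5%. Assumed, because the documents do not say: constant hazard, uniform RAMP-HT enrolment over the six months (mean 0.25 year extra), and no loss to follow-up or competing death.

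**The plan's own figure.** The stated 7,116 per group for 90% power does not reproduce. The usual two-proportion formula with 7% and 8% gives 14,577 per group, and the 8,681 available give 71% power. That is a separate matter; 71% serves here only as the starting point.

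**Formulas.**
- Hazard: λ = −ln(1 − p)/5. For 7%, λ = 0.014514 per year; for 8%, λ = 0.016676.
- Crude RAMP-HT risk: the mean of 1 − exp(−λ(5 + u)), with u uniform on 0 to 0.5 year.
- NNT = 1/(difference in risk).
- Two-sided power: Φ((d − 1.96·s0)/s1) + Φ((−d − 1.96·s0)/s1), where d is the risk difference and s0 and s1 are its pooled and unpooled standard errors.

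**Plan's 7% versus 8%.**
- Cut at 60 months: d = 0.0100, NNT = 100. With s0 = s1 = 0.0040, (0.0100 − 0.00784)/0.0040 = 0.54, so power is 71%.
- Counted to 31 March 2017: 7.337% versus 8.000%, d = 0.00663, NNT = 1/0.00663 = 151. With s0 = s1 = 0.00404, (0.00663 − 0.00792)/0.00404 = −0.32, so power is 38%.

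**No true effect, 8% in both groups.** Crude risks are 8.38% and 8.00%. The standardised difference is 0.00382/0.00416 = 0.92, so the test rejects with probability Φ(0.92 − 1.96) + Φ(−0.92 − 1.96) = 15%. A simulation of 20,000 replicates gave 15.2%, of which 15.1 points were against RAMP-HT.

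**Sensitivity to the enrolment pattern.** The fixed values below apply one extra time to every RAMP-HT patient; 0 and 0.5 year are the limits set by the dates.

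| Extra time for RAMP-HT | Crude RAMP-HT risk (true 7%) | NNT | Power | Rejection if no effect |
|---|---|---|---|---|
| 0 | 7.00% | 100 | 71% | 5% |
| 0.1 year | 7.13% | 116 | 58% | 7% |
| Uniform, mean 0.25 year | 7.34% | 151 | 38% | 15% |
| 0.4 year | 7.54% | 217 | 21% | 31% |
| 0.5 year | 7.67% | 305 | 13% | 44% |

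**Observed 1-year rates carried forward at constant hazard.** The 5-year risks are 1 − (1 − 0.0133)^5 = 6.48% and 1 − (1 − 0.0176)^5 = 8.50%, so the NNT is 50. Counted to 31 March 2017, RAMP-HT becomes 6.79% and the NNT 59 (53 to 66 for 0.1 to 0.4 year extra). Power stays at about 99% under uniform enrolment.

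**Masking.** At 8% in usual care, a true hazard ratio of about 5.00/5.25 = 0.95 would show as no crude difference.

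**The case against.** The best defence is that the outcome and analysis sections speak of 5-year incidence and 5-year rates, which ordinarily means risk at five years. On that reading the section on data extraction only describes the observation window, and 31 March 2017 was chosen so that the last enrolled patient reaches month 60. The cost section also counts 60 months from each patient's own start. This reading is possible, but it is written nowhere, and the data extraction section itself attaches the 5-year label to a span of five and a half years. An analyst following that text would count RAMP-HT events after month 60.

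Second, the plan says effectiveness will be measured by the hazard ratio, and the chi-square test appears among the descriptive comparisons. That stands and limits the damage: the hazard ratio, and the adjustment of the Markov transition probabilities taken from it, are not affected. It does not protect the primary incidence comparison or the NNT.

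Third, this bias runs against the programme, so by itself it will hardly ever produce a false claim of benefit. That is true, but an understated benefit is still a wrong estimate.

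Fourth, the 38% power figure depends on the scenario. Agreed: with the 1-year rates carried forward, significance is practically untouched. The programme was launched only in October 2011, so enrolment may have been weighted to later months. A linear ramp-up, with a mean of 2 extra months, gives NNT 129, power 49% and null rejection 9%. The NNT is still raised whenever there is a true benefit and any mean extra follow-up.

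**Conclusion.** The concern holds and should be fixed. The imbalance of 0 to 6 months follows directly from the stated dates. It biases the crude CVD test and the NNT against RAMP-HT if the plan is followed as written. The size is less certain. On the plan's 7% and 8%, with constant hazards and uniform enrolment, a third of the risk difference is lost (0.66 instead of 1.00 point). On the 1-year rates carried forward, the NNT shifts by about 9 and the significance test hardly changes.

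This says nothing about the net direction of bias in the whole study. Other features act separately, such as the requirement that usual-care patients stay out of the programme up to 31 March 2017.

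**What to change.** State in the outcome and analysis sections that 5-year incidence of CVD, ESRD and death, its between-group test and the NNT count events within 60 months of each patient's own baseline. Either fixed 60-month proportions or Kaplan-Meier (or cumulative incidence) estimates read at 60 months would serve. The Cox and log-rank analyses can keep all follow-up to 31 March 2017.

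The cost is two sentences in the plan and a date rule in the program. Every patient already has 60 months of possible follow-up, so no new data are needed. Under the 7% assumption with uniform enrolment, (0.07337 − 0.07000) × 8,681 = about 29 of 637 RAMP-HT events (4.6%) leave the crude comparison; they stay in the Cox and log-rank analyses.

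A small wording correction can be made at the same time. Read literally, the data extraction section ends observation at the first of any outcome, which would stop mortality follow-up at a CVD or ESRD event. The separate hazard ratios and the yearly costs by complication status suggest this is not meant. Say that each outcome is followed to its own first event, death or the end of follow-up.

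### Read as written, the follow-up rule ends observation at the first of CVD, ESRD or death, which conflicts with the separate 5-year all-cause mortality and ESRD endpoints

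*Combined protocol and SAP*

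**What the plan says.** The follow-up rule stands in section d(iv), under HA CMS Data Extraction of Incidence of HT Complications and All-cause Mortality. The extension to five years is meant "to measure the 5-year incidence of CVD, ESRD and mortality outcomes of these HT patient cohorts". Each patient "will be observed from baseline to the first occurrence of any of the outcome events until 31 March 2017". The numbered list that follows names three outcomes: CVD, ESRD and mortality. The third is unconditional: "Mortality is defined by a documented death in the Hong Kong Death Registry".

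Section d(iii), Outcome Measures, treats these as separate endpoints. Among the secondary outcomes are "The 5-year incidence of end stage renal disease (ESRD) and all-cause mortality among RAMP-HT and usual care HT patients" and "The hazard ratio of CVD, ESRD and all-cause mortalities between" the two groups, together with a number needed to treat for each. Objective 1 and hypothesis 1 in section c also name all-cause mortality and ESRD.

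Section d(v), Long Term Effectiveness of RAMP-HT, states: "The number needed to treat to reduce one CVD, each specific HT complication and death by RAMP-HT will be calculated". These numbers are "calculated from the unadjusted 5-year rates between RAMP-HT and usual care HT cohorts". The Cox models take as outcome the "dependent variable of each first HT complication event". That section gives no censoring rule for any endpoint and no method for competing events.

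**The concern.** One rule is set for all three outcomes, and it stops at whichever comes first. A patient who has a stroke in 2013 and dies in 2015 leaves observation in 2013, and the death is not seen. A patient with CHD in year 1 and ESRD in year 4 loses the ESRD in the same way, and a patient with ESRD first loses any later CVD. What remains is death, or ESRD, as a first event. That is a different quantity from 5-year all-cause mortality or 5-year ESRD incidence.

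Preventing CVD is a main route by which the programme could reduce deaths, so deaths after a survived CVD event bear directly on hypothesis 1. The loss is also expected to be unequal, because the plan anticipates more CVD under usual care. And since the number needed to treat for death comes from unadjusted rates, any missed deaths pass straight into it.

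**Working it through.** **No stated figure to reproduce.** The plan gives no expected mortality or ESRD rate, and none of its figures depends on the rule. The inputs taken from it (Sample size calculation, section d(ii)) are 5-year CVD of 7% (RAMP-HT) and 8% (usual care), and 8,681 patients per group.

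**Step 1: patients who leave observation at CVD.** Number = group size × CVD incidence.
- RAMP-HT: 8,681 × 0.07 = 607.7, about 608.
- Usual care: 8,681 × 0.08 = 694.5, about 694.
- Together about 1,302.

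Some of these first events will be fatal. Those deaths still count, so the next step concerns only later deaths.

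**Step 2: deaths missed.** Let s be the share of CVD patients who survive the first event and die before 31 March 2017. The documents give no value; 10% to 30% is assumed, equal in both groups. Deaths missed per 100 patients = CVD incidence × s.

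| s | RAMP-HT, per 100 (deaths) | Usual care, per 100 (deaths) | Difference removed (points) |
|---|---|---|---|
| 10% | 0.7 (61) | 0.8 (69) | 0.1 |
| 20% | 1.4 (122) | 1.6 (139) | 0.2 |
| 30% | 2.1 (182) | 2.4 (208) | 0.3 |

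The last column is the part of a true difference in crude 5-year mortality (usual care minus RAMP-HT) that the rule would hide.

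**Step 3: how far this depends on equal shares.** With shares s1 (RAMP-HT) and s2 (usual care), the difference removed is 8·s2 − 7·s1 points, with the shares as fractions. It is zero when s1 = (8/7)·s2, for example 22.9% against 20%. A modestly higher later fatality in the RAMP-HT group would therefore cancel the bias, and a larger excess would reverse it.

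**Step 4: cross-check with a three-state model (no CVD, CVD, dead).** Constant hazards over 5 years are assumed.
- CVD hazard: λ = −ln(1 − p)/5, with p = 0.07 or 0.08.
- Death hazard without CVD: m = −ln(1 − M)/5, with M assumed to be 3%, 5% or 8%.
- Death hazard after CVD: k·m, with k assumed to be 3 to 10.
- m and k are the same in both groups, so the programme acts on death only through CVD.

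With a = m + λ:
- deaths before CVD = (m/a)(1 − exp(−5a));
- deaths after CVD = λ[(1 − exp(−5a))/a − (exp(−5a) − exp(−5km))/(km − a)].

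| M, k | All deaths, RAMP-HT / usual care | Deaths before CVD, RAMP-HT / usual care | Deaths missed, RAMP-HT / usual care |
|---|---|---|---|
| 3%, 3 | 3.205% / 3.235% | 2.894% / 2.879% | 27 / 31 |
| 8%, 10 | 9.931% / 10.210% | 7.721% / 7.680% | 192 / 220 |

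The difference in all deaths runs from +0.03 to +0.28 points. The first-event count gives about −0.015 to −0.04. The part hidden is therefore about 0.05 to 0.32 points, the same order as in step 2.

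**The case against.** The strongest reply is that the sentence is loosely worded and that the first occurrence of each outcome, separately, was meant. Several places support this:
- Mortality is defined as any registered death, with no condition on earlier complications.
- The outcome list gives separate incidences, hazard ratios and numbers needed to treat.
- The analysis section refers to each first complication event and to a set of models, which suggests one time variable per outcome. It also reports HT-related mortality, which would make little sense if deaths after a complication were cut off.
- Direct Medical Costs of HT patients extracts utilisation for every patient to 60 months, and costs are analysed by complication status, which needs data after a complication.

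This stands as evidence of a possible intent, and it rules out the reading that deaths will certainly be lost. It does not settle the matter. No sentence says that follow-up for death or ESRD continues after CVD, the phrase in the Cox paragraph names complications and not death, and the only explicit rule says otherwise. The HA statistics team carries out the extraction, so a literal reading could shorten the dataset itself.

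A reader might also infer that the Cox models censor patients at CVD informatively. The analysis section states no censoring rule, so this follows only if the data-collection sentence governs the models.

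A reader might infer, too, that the mortality endpoint turns into non-cardiovascular or complication-free death. The documents do not support that: the CVD definition includes coronary death, sudden death and fatal stroke, so a fatal first event can count as both CVD and death.

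Finally, a first-event rule suits the Markov model, which allows one complication per lifetime and takes mortality after a complication from the literature. That is correct, but it does not justify the rule for the clinical endpoints.

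**Conclusion.** The conflict is real: the observation rule as written cannot deliver the 5-year all-cause mortality and ESRD endpoints as defined. About 608 and 694 patients would leave observation for death and ESRD at their CVD event, if the plan's 7% and 8% hold. The consequence for mortality is illustrative only: 61–182 and 69–208 deaths missed, and a benefit understated by about 0.1–0.3 points. It rests on an assumed 10% to 30% later fatality, equal in both groups, and on usual care having more CVD.

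Two stronger conclusions are not supported. The reversed sign in the cross-check amounts to roughly 1 to 3 deaths per 8,681 and depends on an effect acting only through CVD, so it does not show that the mortality result would be reversed. Nor is the main analysis undermined: the primary CVD outcome is affected only through earlier ESRD, and the cost-effectiveness ratio does not use cohort deaths after CVD. The main effect is on secondary outcomes and on the mortality and ESRD parts of hypothesis 1.

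**What to change.** Replace the single sentence in section d(iv) with a rule for each endpoint:
- **All-cause mortality:** from baseline to death or 31 March 2017, whatever complications came earlier.
- **ESRD:** from baseline to first ESRD, death or 31 March 2017, regardless of earlier CVD.
- **CVD:** from baseline to first CVD, death or 31 March 2017, regardless of earlier ESRD.
- **First complication of any kind:** keep the present rule, only for the Markov transitions.

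Repeat these rules in Long Term Effectiveness of RAMP-HT, and state there how death is handled in the ESRD and CVD analyses. If CHD, heart failure and stroke are each to be reported as a first occurrence, say that each is followed past the others.

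The cost is about a paragraph of wording. The Death Registry is already the source for mortality, and utilisation is already extracted to 60 months for each patient, so no new source is needed. The text should be settled before the 5-year extraction, which the timeline places in April to November 2017. The confirmation of the data schema with the HA statistics team, planned for April to July 2016, is the natural point.

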The Markov models will be analysed by the TreeAge Pro Suite (TreeAge Software, Inc, Williamstown, MA) which can run Markov models.

Data sources are summarized in the table below:

Propose	Item/ unit	Data collection methods
Effectiveness	Incidence of CVD, ESRD and all-cause mortality	Anonymous 5-year dataset of diagnosis record (ICPC-2 and ICD-9-CM) to be extracted by HA statistics team from the HA CMS database #
Direct Medical Costs	(i)Cost of RAMP-HT	(i) In-depth costing of RAMP-HT by 

- set-up and operation costs questionnaires to be completed by HA clusters, GOPCs

- central administration cost questionnaire completed by

	
(ii)Public medical costs of RAMP-HT and usual care group; with complications and without complications
 
(iii)Private direct medical costs
	
Finance Office in HA Head Office
 
(ii)Public healthcare service cost will be estimated by the products of :
 
 
- Public healthcare service utilization rates will be extracted from the 5-year HA CMS dataset.
 
- Unit cost of each healthcare service published in the HKSAR Government Gazette
 
 
(iii)Private medical cost questionnaire administered by telephone survey on 230 RAMP-HT and 218 usual care HT subjects

Calculation of quality adjusted life years (QALY)	SF-6D Health preference values of HT patients without and with complications	SF-12v2 HRQOL data from 410 RAMP-HT and 388 usual care HT patients collected in our previous PRO surveys from May 2013 to March 2014 will be converted to SF-6D preference values.
Cohort Life-time Mortality estimates	
(i) HT related mortality
 
(ii) Mortality from other causes
	
(i)Annual HT-related mortality rates will be estimated from the annual incidence of HT complications and published mortality rates of the respective complications.
 
(ii) Hong Kong standard life table will be used as a

		benchmark for the estimation of mortality from other causes adjusted for age and sex)
--	--	---------------------------------------------------------------------------------------

The Markov modelling will run on the following assumptions:

1. Each HT patient will develop only one HT complication in his/her lifetime.
2. HT patients without complications will not die from HT related death, but may die from other cause of death.

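### The CVD endpoint is meant to include coronary, sudden and stroke deaths, but the only source named for it is CMS diagnosis codes, so a fatal first event never coded in CMS would count as CVD-free

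*Combined protocol and SAP*

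**What the plan says.** - **What the endpoint contains.** Definition 1 in the section on HA CMS data extraction includes under CHD "coronary death or sudden death as indicated by the ICPC-2 K74 to K76 or ICD-9-CM 410.x, 411.x to 414.x, 798.x codes". It continues: "Stroke (fatal and non-fatal stroke) is defined by the ICPC-2 K89 to K91 or ICD-9-CM 430.x to 438.x codes". Five-year CVD incidence is the first primary outcome (Outcome Measures) and the basis of the sample size.
- **Where CVD events come from.** The lead-in to the three definitions follows each patient to the first outcome event, "with CMS documented diagnoses defined by the relevant ICPC-2 and ICD-9-CM codes below". The Effectiveness row of the data sources table covers CVD, ESRD and death from any cause, and names one source for them: "Anonymous 5-year dataset of diagnosis record (ICPC-2 and ICD-9-CM) to be extracted by HA statistics team from the HA CMS database".
- **Where deaths come from.** Definition 3 reads: "Mortality is defined by a documented death in the Hong Kong Death Registry". Cause of death is not mentioned.
- **Cause-specific mortality.** The section Long Term Effectiveness of RAMP-HT will describe "HT-related mortality and all-cause mortalities of the RAMP-HT and usual care cohorts", with no source for the HT-related part. For the Markov model a source is given: "Annual HT-related mortality rates will be estimated from the annual incidence of HT complications and published mortality rates of the respective complications".
- **Care outside the HA.** Private costs cover "private hospitalisation and self-medications inclusive of self-financed medications prescribed by the HA", and they are collected by telephone questionnaire, not from CMS.

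**The concern.** The content of the endpoint and its source do not match. Fatal events are meant to count, but a diagnosis code in CMS arises from contact with the HA. Some deaths at home or in private hospitals may never produce a CVD code. If such a death is the patient's first CVD event, the plan records a death but no CVD, and follow-up for CVD ends at death as a non-event. The reason for leaving follow-up is then the event being studied.

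At stake is complete counting of the most severe events in a primary outcome, and with it the absolute difference and the NNT, which the plan takes from crude 5-year rates. The Markov model also draws its transition probabilities from the observed complication rates and assumes that patients without a complication do not die of HT. An uncoded fatal first event would therefore be absent from those transition probabilities too.

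**Working it through.** **1. The plan's own figure.** The sample size section gives 7,116 per group for 7% versus 8%, 90% power and 5% significance. The usual two-proportion formula, two-sided, is

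n = [1.960·√(2·0.075·0.925) + 1.282·√(0.07·0.93 + 0.08·0.92)]² / 0.01² = 14,577 per group.

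So 7,116 is not reproduced. That is a separate matter and does not bear on this point. It is shown because power below is computed at the 8,681 per group actually available:

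Φ{[0.01·√8,681 − 1.960·√(2·0.075·0.925)] / √(0.07·0.93 + 0.08·0.92)} = 70.6%.

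**2. Sources side by side.**

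| Outcome | Diagnosis codes | Other source named |
|---|---|---|
| CVD, including fatal CVD | ICPC-2, ICD-9-CM | none |
| ESRD | ICD-9-CM | eGFR below 15 |
| All-cause mortality | none | Death Registry, fact of death |

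Where the definitions use something other than a code, they say so. For CVD they do not.

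**3. Who is affected.** Only patients whose first CVD event is fatal and who never receive a CMS code for it. A patient with an earlier coded event is already counted, and a death in an HA hospital or A&E department may be coded.

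**4. Size.** The documents give none of the three inputs needed, so all are assumptions: 5-year mortality 4-6%, share of deaths from CHD, heart failure or stroke 20-30%, share of those uncoded 20-40%.

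- Low: 0.04 × 0.20 × 0.20 = 0.16%; × 8,681 = 14 per arm.
- High: 0.06 × 0.30 × 0.40 = 0.72%; × 8,681 = 63 per arm.
- Expected events: 0.07 × 8,681 = 608 (RAMP-HT); 0.08 × 8,681 = 694 (usual care).
- Share: 14/694 = 2.0% to 63/608 = 10.4%.

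**5. Effect if the same share is missed in both arms**, reading 7% and 8% as true incidence and multiplying each by (1 − share):

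| Share missed | RAMP-HT | Usual care | Difference (points) | Risk ratio | NNT | Power at 8,681 |
|---|---|---|---|---|---|---|
| 0% | 7.00% | 8.00% | 1.00 | 0.875 | 100 | 70.6% |
| 5% | 6.65% | 7.60% | 0.95 | 0.875 | 105 | 68.2% |
| 10% | 6.30% | 7.20% | 0.90 | 0.875 | 111 | 65.7% |
| 20% | 5.60% | 6.40% | 0.80 | 0.875 | 125 | 60.2% |

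The 20% row lies beyond the range in step 4 and is shown as an outer case. Equal loss here means an equal proportion. If instead the same 0.72% of each cohort were missed, the difference would stay at 1.00 point and the risk ratio would be 6.28/7.28 = 0.863.

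**6. Effect if the shares differ.**

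- RAMP-HT 5%, usual care 10% missed: 6.65/7.20 = 0.924.
- RAMP-HT 10%, usual care 5% missed: 6.30/7.60 = 0.829.

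**7. If 7% and 8% already omit these deaths.** They are projected from the earlier quality-of-care study, whose cohorts came from CMS data. In that case full capture adds events. Adding 0.2-1.0 points in usual care at the same risk ratio gives 71.7-76.0% power; adding the same points to both arms gives 69.5-65.6%.

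**The case against.** The strongest reply is that the text does not prove the gap. The lead-in about CMS diagnoses introduces all three definitions, and two of them use other data, so it is not exclusive by itself. The Effectiveness row is a summary that places all-cause mortality under the CMS diagnosis record, contrary to definition 3. Sudden-death codes are listed on purpose, so the authors expected fatal events in the data. The data schema in Appendix F is not in the text available here, and it may hold a cause-of-death field; the separate mention of HT-related mortality would fit that. These deaths also still count in all-cause mortality, a secondary outcome with its own hazard ratio and NNT.

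Much of this stands. It rules out three stronger readings that a reader might infer:

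- **That every death at home or in a private hospital lacks a CMS code.** No section says so, nor whether CMS receives causes of death from the registry.
- **That the bias runs against RAMP-HT**, because its patients are recalled every 12-24 months. That interval is a Markov assumption, usual-care patients are also drawn from HA clinics, and nothing shows that they leave HA care more often.
- **That planned power is overstated for this reason.** The 7% and 8% may already exclude such deaths.

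What the reply does not remove is that definition 1 names no source for fatal CVD other than CMS codes, and definition 3 uses the registry for fact of death alone.

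**Conclusion.** The point holds as a mismatch between the stated content of a primary endpoint and its stated source. Applied as written, the rule treats a fatal first CVD event without a CMS code as freedom from CVD. The loss is 14-63 events per arm, about 2-10% of expected events, but only under the assumptions in step 4. At 10% missed equally, the difference falls to 0.90 points and the NNT rises from 100 to 111, with the risk ratio unchanged. The direction of any bias from unequal loss is unknown. The study is not invalidated, but the rule should be changed before the 5-year extraction, since the registry is already one of the plan's sources.

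**What to change.** - In definition 1, also count as a CVD event any Death Registry death whose underlying cause is CHD, heart failure, sudden death or stroke, dated at death. State the registry's coding version and give its mapping to the groups already listed.
- Confirm that cause of death is in the extraction schema (Appendix F), or add it if absent. Name the registry in the Effectiveness row of the data sources table.
- Use the same field to define the observed HT-related mortality in the section on long-term effectiveness.
- Report the CMS-code-only definition as a sensitivity analysis, so that the effect of the change is visible by arm.

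The cost is one field and a code mapping, but release of the field with an anonymous extract must be arranged with the data provider. Some certified causes of death are inaccurate. The change does not recover non-fatal events treated only outside the HA.
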